# **11. STATISTICAL CONSIDERATION**

A formal Statistical Analysis Plan (SAP) will be developed and finalized prior to locking the database. The full details of data presentation and analyses will be provided in SAP.

Additional statistical analyses other than these described in this section may be performed if deemed appropriate and included in the SAP. Any deviations from the final SAP or from what is outlined in the protocol will be discussed in the final study report (CSR).

# 11.1 Hypothesis

No hypothesis testing is planned for this study.

# **11.2 Sample Size Determination**

A sample size of 125 randomized subjects (50 each in medium and high dose levels and 25 in placebo) in addition to 10 sentinel subjects is not based on formal statistical testing but rather based on clinical judgement and predicted to yield meaningful safety and immunogenicity results. Placebo was added for safety comparison.

# **11.3 Multiplicity Adjustment**

No multiplicity adjustment will be implemented for this study.

## **11.4 Population for Analysis**

For purposes of analysis, the following analysis sets are defined:

#### Table 9:Populations for Analyses

Analysis Population	Description
Screened	All subjects who enter screening (assigned a screening number)
Intent to Treat (ITT)	All subjects who are randomized. The analyses using ITT will be based upon the randomization group allocated.
Per Protocol	All subjects in the ITT set who receive one dose and who have not violated any inclusion/exclusion criteria and / or deviated in a way that could influence their Immunogenicity assessments.

Analysis Population	Description
Safety	All randomized subjects who receive at least 1 dose of the study drug. Subjects will be analyzed according to the treatment (vaccine) they actually received. All safety analyses will be conducted based on the Safety set.
Immunogenicity	All randomized subjects who receive at least 1 dose of the study drug and have at least one valid immunogenicity result after Day 1. Subjects will be analyzed according to the treatment (vaccine) they actually received. All immunogenicity analyses will be conducted based on the Immunogenicity set.

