#### Trial design

This is a multi-center, double-blind, randomized, placebo-controlled, single dose regimen, dose ranging study in healthy volunteers ( $\geq$ 18 years and  $\leq$ 80 years). The study will enroll 10 sentinel subjects in an open label period and randomize 125 subjects in three double-blind arms.

After reviewing and signing an informed consent, the subjects will undergo screening assessments to determine study eligibility up to a 45-day Screening Period.

The first 10 sentinel subjects will receive open label high dose of active vaccine  $(2 \times 10^{11} \text{ IU})$ . If no dose-related toxicities are observed, and upon the recommendation of the Safety Monitoring Committee (SMC) following review of Day 1 through Day 8 safety data, enrollment of the remaining subjects will be initiated. The sentinel subjects will be enrolled in a staggered design, in which no more than two (2) subjects are dosed per 24-hours. All sentinel subjects will be observed on site, for safety at least 2 hours post dose. After the ten (10) sentinel subjects have completed Day 8 post dose, and if no dose-related toxicities are observed, and upon the recommendation of the Safety Monitoring Committee (SMC) following review of safety data up to one week post dose, enrollment of the randomized double-blind study will be initiated. While ten (10) subjects will be dosed in the sentinel group, to allow for dropouts, eight (8) subjects with complete safety data (defined as Day 1 to Day 8) will be enough to convene the SMC.

If pre-established stopping rules are met, enrollment of subsequent subjects will be halted until the SMC has completed the review of all available safety data and provides recommendation for further study conduct.

On Day 1 of the randomized portion, subjects will be randomized in a 2:2:1 ratio to one of the three treatment arms to receive active vaccine or placebo, as follows (Figure 1):

administration (Day 29), and a Follow-up Period of one year for safety and duration of immune response. Study assessments will be conducted as shown in the SoA (Table 1). In addition, subjects will be contacted by phone or app between site visits to monitor for safety as specified in the SoA (Table 1).

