#### **Randomization and Blinding 6.7**

#### **Randomization Procedures** 6.7.1

#### Assignment of a Subject Number:

Each subject who signs informed consent will be assigned a subject number. Only the first 10 sentinel subjects will receive open label high dose of active vaccine ( $2 \times 10^{11}$  IU). Following SMC recommendation on review of sentinel safety data up to and including Day 8, new subjects once deemed eligible and enrolled in the study will also receive a randomization number and treatment assignment, based on the blinded randomization schedule. The subject number will be used as the primary identifier for the complete duration of the study. After the subject signs the informed

Vaxart Inc			
VXA-NVV-202	Version	2.	0

consent form (ICF), the Investigator (or designee) will enter the subject into the sites Screening Log. All screen failed and randomized subjects will have data entered in the study specific EDC.

After signing an informed consent, the subjects in the randomized double blind portion of the study will undergo screening assessments to determine study eligibility up to 45-day for Screening Period. All subjects who sign a study specific informed consent form will have data entered into the EDC. On Day 1, subjects will be randomized in a 2:2:1 ratio to one of the three treatment arms to receive active vaccine or placebo, as follows (Table 7).

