# 7.1.2 Procedure to be followed during Active Study Period (Day 1 to Day 29)

It is anticipated that the procedures below will be conducted in a stepwise manner; ensuring that procedures listed prior to administration of the vaccine are conducted prior to that administration for both the open label and randomized groups of the study.

- The Principal Investigator will ensure that all inclusion criteria and none of the exclusion criteria are met on Day1, prior to vaccination.
- A urine pregnancy test will be done for all female subjects prior to dosing.
- A targeted, and symptom-directed physical examination will be done for all subjects during the active study period visits., At a minimum, assessments of the skin, respiratory system, cardiovascular system, and GI (abdomen, liver and spleen) will be included.
- Vital signs will be obtained, including temperature, sitting blood pressure, pulse rate and respiratory rate after at least 5 minutes of rest to the subject during the active study period.
- The subject's number (open label) or randomization number will be noted.
- Site staff member(s) will dispense/administer the investigational product. Please refer to the Pharmacy Manual for further instruction on this process.
- Prior to study drug administration on Day 1, the subject's temperature (oral) will be measured, and a trained member of the site study staff will dispense the tablet(s) constituting the assigned dose to the subject.
- For the subjects enrolled into the open label sentinel study arm, the site staff must observe the subjects at the site, in the ≥18 to ≤80 years old age group, for at least 2 hours after study drug administration for any acute reactions. Any acute reactions are to be recorded in the subject's source documents, on the AE page of the eCRF, and on a serious adverse event (SAE) form, as applicable.
- For the subjects enrolled into the randomized double blind portion study arm, the site staff must observe the subjects at the site, in the ≥18 to ≤80 years old age group for at least 30

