## **10.2 Safety Monitoring Committee**

The first 10 sentinel subjects will receive open label high dose of active vaccine  $(2 \times 10^{11})$  in a staggered manner, no more than two (2) subjects dosed in a 24-hour period. All subjects dosed will be observed for a minimum of 2 hours post dose. While ten (10) subjects will be dosed in the sentinel group, to allow for dropouts, eight (8) subjects with complete safety data (defined as Day 1 to Day 8) will be enough to convene the SMC. If no dose-related toxicities are observed, and upon consideration of the SMC recommendations following review of safety data, enrollment of the randomized double-blind study will be initiated.

Alternatively, if pre-established stopping rules are met, enrollment of subsequent subjects will be halted until the study SMC has completed a review of all available safety data and offers a recommendation to proceed.

If any of the events described below are met during the overall conduct of the study (open label and randomized phase), the study will be halted, and no new randomization/vaccinations will be allowed pending an SMC safety review

- One or more subjects experiences a treatment-related serious adverse event (SAE) of any grade
- Two or more subjects experience the same treatment-related grade ≥3 solicited symptom within one week following vaccination.
- Two or more subjects experience the same treatment-related unsolicited grade ≥3 AE between Day 1 and Day 29 (Active Period).

The SMC will provide study oversight throughout the duration of the trial active and safety follow-up periods (Day 1 through Day 365 post-vaccination).

The IRB, US FDA-CBER will be notified if the study is halted for safety concerns.

A SMC will be created to provide oversight of the conduct of the trial to ensure the safety of subjects and the validity and integrity of study data. The committee will consist of independent physicians and/or scientists with vaccine clinical trials experience or expertise, and the Medical Monitor, who does not enroll subjects into the study. Please refer to the study specific SMC for details.

The SMC will function in accordance with the following provisions: (1) United States (US) Code of Federal Regulations (CFR) applicable to clinical studies (21 CFR Part 50, 21 CFR Part 54, 21 CFR Part 312.55 and 312.56. (2) ICH E6 and 62 Federal Register 25691 (1997): Good Clinical Practice (GCP) Consolidated Guideline.

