#### **11.5.2** Analysis of the Primary Safety End Points

Safety will be summarized for the safety set (active vs. placebo). Solicited Symptoms of Reactogenicity, unsolicited AEs, SAEs, physical examination, and vital signs will be summarized descriptively by treatment group and study visit.

Endpoint	Statistical Analysis Methods
Primary (measured	Frequency, duration, and severity of Solicited Symptoms of Reactogenicity (local, systemic) measured daily for 1 week following vaccination.
from Day 1 through Day 29)	Frequency, duration, and severity of unsolicited AEs, and SAEs through the active period (4 weeks post last dose).
	Descriptive statistics will be provided for each reactogenicity endpoint for each dose. Local reactions and systemic events from Day 1 through Day 8 after each dose will be presented by severity and cumulatively across severity levels.

Analyses will be performed for the total set (active vs. placebo).

	Descriptive summary statistics will include counts and percentages of subjects with the indicated endpoint and the associated Clopper-Pearson 95% CIs. AEs will be categorized according to the Medical Dictionary for Regulatory Activities (MedDRA ® ) terms. Descriptive summary statistics (counts, percentages, and associated Clopper-Pearson 95% CIs) will be provided for any TEAEs for each vaccine group as well as the placebo group. SAEs will be categorized according to MedDRA ® terms. The safety analyses are based on the safety set. Subjects will be summarized by vaccine group and placebo according to the study drug they actually received. Missing reactogenicity Diary data will not be imputed; missing TEAE dates will be handled according to the rules determined in the SAP.
Exploratory (measured from Day 30 through Day 365)	Frequency, duration, and severity of SAEs, AESIs and NOCIs for 1 year following the study drug dose.

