#### 11.5.6 Tabulation of Individual Subject Data

By subjects listing will be produced for each variable by treatment group and study visit.

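### The Safety set admits only randomized subjects, so the 10 open-label high-dose sentinels are missing from every planned safety summary table

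*Combined protocol and SAP*

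**What the plan says.** - **Safety set.** Table 9 (section 11.4) defines it as "All randomized subjects who receive at least 1 dose of the study drug. Subjects will be analyzed according to the treatment" actually received, and assigns all safety analyses to it. Section 11.5.2 repeats the link: "The safety analyses are based on the safety set".
- **Sentinels are not randomized.** Ten subjects receive the high dose open label, and 125 others are later randomized 2:2:1. Under section 6.7.1, it is after the SMC has reviewed the sentinel data that "new subjects once deemed eligible and enrolled in the study will also receive a randomization number and treatment assignment". Section 7.1.2 keeps the two identifiers apart: "The subject's number (open label) or randomization number will be noted".
- **Sets that contain them.** Of the Table 9 sets, the sentinels meet only the Screened definition, "All subjects who enter screening (assigned a screening number"), and no safety analysis uses that set. The ITT set, which section 11.5.5 uses for subgroup summaries, is also limited to randomized subjects.
- **Elsewhere they count as study subjects.** Table 3 includes them in the total of 135, Table 7 gives them an arm column, and the synopsis lists them beside Arm 2. Footnote g of the Schedule of Activities keeps them in the active and follow-up periods. The halting rules in section 10.2 apply "during the overall conduct of the study (open label and randomized phase").
- **Other routes for their data.** The synopsis makes the start of randomized enrollment depend on an SMC recommendation "following review of Day 1 through Day 8 safety data". Section 14.1 has the sentinel safety data summarized for that review. Section 11.5.6 says "By subjects listing will be produced for each variable by treatment group and study visit" and names no analysis set.

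**The concern.** A safety population normally contains everyone who took the product. Here the restriction to randomized subjects removes a group given the highest dose, while the primary objective is to select the dose with which to proceed safely.

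Two consequences follow. First, a sentinel event can count toward a study halt under section 10.2 and yet enter no tabulated rate. Second, the named sentinel review stops at Day 8, whereas the primary unsolicited-AE window runs to Day 29 and the SAE, AESI and NOCI window to Day 365. Sentinel events after Day 8 fall outside both that review and the section 11 tables.

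There is also a timing issue. Sentinel results are open label and are reviewed before randomized enrollment begins, but the SAP need only be final before database lock and unblinding. If the question is left to the SAP, whether to tabulate the sentinels could be decided after their results are known.

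**Working it through.** **Inputs.** From section 11.2 and Table 3: 10 sentinels (high dose), 125 randomized. From the randomization ratio: 2:2:1. From section 11.5.2: Clopper-Pearson 95% intervals. From section 11.1: no hypothesis test, so no power calculation applies. The true event rates of 1%, 2% and 5% used below are assumptions; the plan gives none.

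**Step 1: the plan's own counts.** 125 × 2/5 = 50, 125 × 2/5 = 50, 125 × 1/5 = 25; and 10 + 50 + 50 + 25 = 135. These match Table 3.

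**Step 2: who is left out.** If all planned subjects are dosed, the Safety set as worded holds 125 of 135.
- High dose: 10/(10 + 50) = 16.7% omitted.
- All vaccinees: 10/(10 + 50 + 50) = 9.1% omitted.
- All planned subjects: 10/135 = 7.4% omitted.

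**Step 3: precision with no events.** The two-sided 95% Clopper-Pearson upper limit is 1 − 0.025^(1/n).

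| Group | n | Upper limit for 0/n |
|---|---|---|
| Sentinels alone | 10 | 30.8% |
| High dose, randomized only | 50 | 7.1% |
| High dose, all dosed | 60 | 6.0% |
| Vaccinees, randomized only | 100 | 3.6% |
| Vaccinees, all dosed | 110 | 3.3% |

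**Step 4: chance of seeing at least one high-dose event**, 1 − (1 − p)^n.

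| Assumed true rate p | n = 50 | n = 60 |
|---|---|---|
| 1% | 39.5% | 45.3% |
| 2% | 63.6% | 70.2% |
| 5% | 92.3% | 95.4% |

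**Step 5: a hypothetical case.** Suppose one sentinel and one randomized high-dose subject have the same treatment-related grade 3 unsolicited AE within the active period. Two subjects meet the section 10.2 criterion for a halt. The section 11 table would show 1/50 = 2.0% (95% CI 0.05% to 10.6%). Reporting everyone dosed would show 1/10 and 1/50 side by side, and 2/60 = 3.3% (0.4% to 11.5%) for all high-dose recipients. The interval hardly moves, but one of the two events behind the halt is missing from the planned table.

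**Step 6: time not covered by the named sentinel review.** Days 9 to 29 are 21 of the 29 active-period days, followed by the remaining follow-up to Day 365.

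**The case against.** The strongest case on the other side is that this is a reporting clarification with little statistical effect. No hypothesis is tested. No between-arm contrast should use the sentinels in any event, since they are open label, not randomized, and have a different on-site observation time and Day 8 window. The upper limit moves only from 7.1% to 6.0%. These points stand, and they bound the size of the harm.

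It can also be said that the data will not vanish. Section 14.1 has sentinel safety data summarized for review, SMC oversight runs to Day 365, the clinical study report rests on the Day 29 dataset with an addendum for follow-up, and listings are planned. This makes it unlikely that a serious event goes unseen. But none of these routes is a planned section 11 rate or confidence interval. The count of 21 days is calendar time, not a measure of risk, and the other primary safety endpoint, solicited symptoms, lies within the Day 1 to Day 8 review.

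Third, the SAP is still to be written and may describe the sets differently; sections 11 and 11.5.1 leave it room to do so. Final handling therefore cannot be judged from these documents. What can be judged is that section 11 hands the SAP an explicit definition that excludes the sentinels.

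Finally, the exclusion may be unintended. Tables 3 and 7 treat the sentinels as a treatment group, and section 11.5.2 also refers to a total set. That term is undefined, however, and the same section names the safety set as the basis. Unintended or not, the wording excludes them.

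**Conclusion.** The concern holds. Followed as written, Table 9 and section 11.5.2 leave the 10 sentinels out of every section 11 safety summary, which is 16.7% of those given the high dose and 9.1% of all vaccinees. This is an explicit rule that conflicts with the rest of the protocol, not merely a missing detail.

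The consequence is incomplete tabulated safety reporting at the highest dose, with a modest loss of precision. It is not a likely failure to detect a serious event, and it does not bias the randomized comparisons. The proportions assume that all 135 planned subjects are dosed; the detection probabilities rest on the assumed event rates.

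**What to change.** 1. In Table 9, define the Safety set as all subjects, sentinel or randomized, who receive any study drug, analyzed by treatment received. Carry this into the SAP, preferably before sentinel results are known.
2. In the safety tables, show sentinel high dose, randomized medium dose, randomized high dose and placebo in separate columns.
3. Optionally add a supplementary column for all high-dose recipients (n = 60), labelled as mixing open-label and blinded data.
4. State that all between-arm comparisons, against placebo and between doses, use the randomized arms only, because only the high dose has open-label subjects.
5. State in section 11.5.6 that the listings include the sentinels.

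The cost is a revised definition, a statement on comparisons, a line on listings and one or two table columns, with no new data, visits or subjects. The one drawback is that sentinel symptom reports are open label and collected under somewhat different conditions; the separate column and the randomized-only comparisons deal with that.

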#### 11.5 Statistical Analysis Plan

#### 11.5.1 General Approach

The SAP will be developed and finalized before database lock and breaking the blind for any of the planned analyses. It will describe the subject sets to be included in the analyses and the procedures for accounting for missing, unused, and spurious data. This section provides a summary of the planned statistical analyses of the primary endpoints.

#### **11.5.2** Analysis of the Primary Safety End Points

Safety will be summarized for the safety set (active vs. placebo). Solicited Symptoms of Reactogenicity, unsolicited AEs, SAEs, physical examination, and vital signs will be summarized descriptively by treatment group and study visit.

Endpoint	Statistical Analysis Methods
Primary (measured	Frequency, duration, and severity of Solicited Symptoms of Reactogenicity (local, systemic) measured daily for 1 week following vaccination.
from Day 1 through Day 29)	Frequency, duration, and severity of unsolicited AEs, and SAEs through the active period (4 weeks post last dose).
	Descriptive statistics will be provided for each reactogenicity endpoint for each dose. Local reactions and systemic events from Day 1 through Day 8 after each dose will be presented by severity and cumulatively across severity levels.

Analyses will be performed for the total set (active vs. placebo).

	Descriptive summary statistics will include counts and percentages of subjects with the indicated endpoint and the associated Clopper-Pearson 95% CIs. AEs will be categorized according to the Medical Dictionary for Regulatory Activities (MedDRA ® ) terms. Descriptive summary statistics (counts, percentages, and associated Clopper-Pearson 95% CIs) will be provided for any TEAEs for each vaccine group as well as the placebo group. SAEs will be categorized according to MedDRA ® terms. The safety analyses are based on the safety set. Subjects will be summarized by vaccine group and placebo according to the study drug they actually received. Missing reactogenicity Diary data will not be imputed; missing TEAE dates will be handled according to the rules determined in the SAP.
Exploratory (measured from Day 30 through Day 365)	Frequency, duration, and severity of SAEs, AESIs and NOCIs for 1 year following the study drug dose.

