#### Table 2: **Sentinel Subjects**

GII.4/GI.1 vaccine

\*Two (2) subjects can be dosed in a staggered manner, at least 24 hours from the dosing date of the last 2 subjects

If pre-established stopping rules are met, enrollment of subsequent subjects will be halted until the SMC has completed the review of all available safety data and provides recommendation for further study conduct.

On Day 1 of the double-blind portion, subjects will be randomized in a 2:2:1 ratio to one of the 3 study arms to receive active vaccine or placebo, as follows (Table 3):

Treatment Group	Study drug	Per Strain Dose (IU)	Total Dose (IU/dose)	Dosing Schedule	No of Subjects
Sentinel Open Label	Bivalent GII.4/GI.1 vaccine	1×10 	2×10 	Day 1	10
Arm 1	Bivalent GII.4/GI.1 vaccine	5×10 	1×10 	Day 1	50
Arm 2	Bivalent GII.4/GI.1 vaccine	1×10 	2×10 	Day 1	50
Arm 3	Placebo	N/A	N/A	Day 1	25
Total					135

Table 3: **Study Design** 

Abbreviations: IU=infectious units; N/A=not applicable

After vaccination on Day 1, the study will include an Active Study Period that runs through 4 weeks after administration (Day 29), and a Follow-up Period of one year for safety and duration of immune response. Study assessments will be conducted as shown in the SoA (Table 1). In addition, subjects will be contacted by phone or app between site visits to monitor for safety as specified in the SoA (Table 1).

A subject is considered to have completed the study if he/she completes the study active period at Day 29 (End of Study Active Period). Following completion of the Day 29 visit by all subjects the database will be cleaned and locked and the study unblinded. The Clinical Study Report (CSR will be written based on the Day 29 dataset.

A subject is considered to have completed the Follow-up Period if he/she remains in the study through Day 365 (Month 12). Following completion of the Day 365 a tele-health appointment phone contact will be conducted for all subjects, the safety database will be cleaned and locked, and data collected during the Follow-up Period will be included in a CSR addendum.

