## 4.2 Scientific Rationale of Trial Design

This study is designed as a standard double-blind placebo-controlled single administration, doseranging study to evaluate the effect of 2 different doses (high and medium dose) of VXA-GII.4-NS plus VXA-G1.1-NN in the target population, compared with placebo.

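### The protocol calls the safety analysis active versus placebo but specifies only within-group intervals; a descriptive between-group difference with its interval should be named before unblinding

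*Combined protocol and SAP*

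**What the plan says.** - **Purpose of placebo.** Section 11.2: "Placebo was added for safety comparison". Section 4.2 describes a design to "evaluate the effect of 2 different doses (high and medium dose"), each set against placebo.
- **Decision to be supported.** Section 3.1.1 makes safety and immunogenicity jointly the basis for choosing the dose to take into Phase 3.
- **Size.** Section 11.2: "A sample size of 125 randomized subjects (50 each in medium and high dose levels and 25 in placebo"), a number that "is not based on formal statistical testing but rather based on clinical judgement".
- **Safety method.** Section 11.5.2 twice describes the summaries as active against placebo. What it specifies is counts, percentages and exact one-sample intervals: "associated Clopper-Pearson 95% CIs) will be provided for any TEAEs for each vaccine group as well as the placebo group". It names no risk difference, ratio or interval for a contrast.
- **Dose comparison.** Section 11.5.3 says the two active groups will be compared on immunogenicity. Section 11.5.2 has no matching statement for safety.
- **Inferential stance.** Section 11.1: "No hypothesis testing is planned for this study". Section 11.3: "No multiplicity adjustment will be implemented for this study".
- **What is deferred.** Section 11 leaves full analysis details to a separate SAP and allows that SAP to add analyses. Section 11.5.1 calls the protocol text a summary and requires the SAP to be final before database lock and unblinding.

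**The concern.** A comparison is named as the reason for an arm, but no quantity is named to express it. A Clopper-Pearson interval describes one arm. It does not say how uncertain the difference between two arms is, and that uncertainty is considerable when one arm has 25 subjects. If the tables show only by-arm intervals, a reader who sees them overlap may conclude that the arms are compatible with no difference when the data say otherwise. The same applies to high against medium dose, where safety is half of the dose-selection objective. If the contrast is not fixed before the blind is broken, any difference reported later will look chosen after the fact.

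**Working it through.** **Inputs from the documents.** Arm sizes are 50, 50 and 25 (Section 11.2), and "subjects will be randomized in a 2:2:1 ratio to one of the 3 study arms" (Section 4.1). These agree: 125 × 2/5 = 50, 125 × 2/5 = 50, 125 × 1/5 = 25. The current text has no power or precision figure to reproduce.

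**Assumed inputs.** The documents give no expected event rates for this trial. Every count and rate below is an assumption, chosen to show the range.

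**Formulas.**
- By-arm: Clopper-Pearson 95% limits from beta quantiles, B(0.025; x, n−x+1) and B(0.975; x+1, n−x).
- Difference: Newcombe's interval. With p1, p2 the observed proportions, d = p1 − p2, and (l, u) the Wilson 95% limits of each arm:
  - lower = d − √[(p1 − l1)² + (u2 − p2)²]
  - upper = d + √[(u1 − p1)² + (p2 − l2)²]

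**Step 1. Dose against placebo, 22/50 and 5/25.**
- By-arm exact intervals: 30.0–58.7% and 6.8–40.7%. They overlap.
- Wilson limits: 31.16–57.69% and 8.86–39.13%.
- Lower = 24 − √(12.84² + 19.13²) = 24 − 23.04 = 1.0.
- Upper = 24 + √(13.69² + 11.14²) = 24 + 17.65 = 41.7 (41.65 before rounding).
- The difference is 24 points, 95% CI 1.0 to 41.7.

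Against 5/25, 22/50 is the smallest vaccine count at which the difference interval lies above zero. The by-arm intervals do not separate until 28/50.

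**Step 2. High against medium, 20/50 and 10/50.** The by-arm intervals overlap (26.4–54.8% and 10.0–33.7%). The difference is 20 points, 95% CI 2.0 to 36.4.

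**Step 3. Smaller excesses and no events.**

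| Counts | Difference (points) | Newcombe 95% CI |
|---|---|---|
| 10/50 vs 5/25 | 0 | −21.0 to 17.1 |
| 15/50 vs 5/25 | 10 | −12.0 to 27.7 |
| 20/50 vs 5/25 | 20 | −2.8 to 37.7 |
| 15/50 vs 10/50 | 10 | −7.0 to 26.3 |
| 0/50 vs 0/25 | 0 | −13.3 to 7.1 |

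The last row is informative in itself: no events in either arm still leaves the difference uncertain by 7 to 13 points.

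**Step 4. How often each display would show the excess** (exact binomial enumeration over all outcomes, assumed true rates).

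| True rates, arm sizes | Difference CI excludes 0 | By-arm CIs separate |
|---|---|---|
| 45% vs 20%, 50/25 | 0.588 | 0.207 |
| 40% vs 20%, 50/50 | 0.595 | 0.211 |
| 30% vs 20%, 50/25 | 0.14 | 0.02 |
| 30% vs 20%, 50/50 | 0.21 | 0.03 |

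The gain in the first two rows does not come from a liberal interval. With equal true rates of 10–40%, the Newcombe interval excludes zero 3.5–5.5% of the time, whereas by-arm intervals separate only about 0.1–0.3% of the time. Separation of by-arm intervals is therefore far stricter than a 95% criterion. In the last two rows both displays usually miss the excess, and the limit is the number of subjects.

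**The case against.** **The trial is openly descriptive.** By-arm exact intervals are a legitimate summary, and the absence of testing is a stated choice. That stands. But a risk difference with its interval is also description, and it needs no test or error-rate allocation.

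**The SAP may already deal with this.** A reader might infer from Section 11.5.2 that no between-group difference will be estimated at all. The documents do not support that, because they defer details to a later SAP and allow added analyses. They support only that the protocol specifies none. The point still matters, because Section 11.5.2 already goes down to the interval method for the primary safety endpoints.

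**The active-against-placebo wording may mean a pooled summary.** It may, so it would be wrong to say that only separate-arm summaries are planned. A pooled summary would still have no stated estimator, and it cannot inform a choice between doses.

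**The plan contains no overlap rule.** This is correct. Step 4 shows what an informal reading by overlap would cost; it does not describe a rule the sponsor adopted. Counts are reported, so anyone can compute the difference and its interval afterwards. What would be missing is a prespecified, visible estimate. Counting how often an interval excludes zero is also close to a test, and is used here only as a measure of how clearly the display shows an excess.

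**The dose contrast is less firmly promised.** The safety comparison in Section 11.2 concerns placebo. The case for high against medium rests on the dose-selection objective, not on an unmet commitment.

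**More intervals mean more chance findings.** True, and a reason to keep the list of endpoints short.

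**Conclusion.** The concern holds in a limited form: the protocol names a safety comparison, specifies only within-group intervals, and leaves the between-group estimate unstated, with the SAP still open. The arithmetic from assumed counts shows that overlapping by-arm intervals can accompany a difference whose 95% interval lies above zero. For assumed true excesses of 20 to 25 points, the difference interval shows the excess roughly 59–60% of the time, against 21% for separation of by-arm intervals. For an assumed 10-point excess the figures are 14% against 2% (dose against placebo) and 21% against 3% (between doses), so a better interval helps little there. All these sizes depend on assumed event rates and on the planned 50/50/25 split. This is a cheap improvement to a descriptive plan. It is not a flaw that invalidates the safety analysis.

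**What to change.** Keep the by-arm Clopper-Pearson intervals. In Section 11.5.2, and in the SAP before unblinding, add risk differences with two-sided 95% score-type intervals (Newcombe or Miettinen-Nurminen; name one) for:
- high dose vs placebo
- medium dose vs placebo
- high vs medium dose

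Restrict them to four summary endpoints: any solicited symptom, any solicited symptom of Grade 3 or higher, any unsolicited AE, and any related unsolicited AE. State that the intervals are descriptive, without testing or multiplicity adjustment, so Sections 11.1 and 11.3 stand unchanged. Say also whether the active-against-placebo wording means pooled doses, each dose, or both.

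**Cost.** A sentence or two of text and three added columns in one safety table. No subjects, visits or procedures are added. The downside is 4 × 3 = 12 more unadjusted intervals. If the arms truly do not differ, each excludes zero about 2–5.5% of the time (assumed event rates of 5–40%), so about 12 × 0.02 = 0.2 to 12 × 0.055 = 0.7 chance exclusions are expected in total. A table footnote should say so.
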